**Overall Survival**

Overall Survival is defined as the duration from the start of first line standard of care systemic therapy to the date of death or date of last contact; those lost to follow-up will be censored.

**9.0 Adverse Events List and Reporting Requirements**

**9.1 Adverse Event List for Radiotherapy**

Risks and side effects related to the SBRT	
More common (>10% of patients): 
 
Damage to surrounding normal lung and/or collapse of a portion of treated lung
 
Cough
 
Increased phlegm production
 
Changes in the lungs as the tumor shrinks; these changes will be recognized by your radiation doctor on your x-rays or scans as expected "scarring" that is developing. In most patients, no noticeable symptoms will result from this lung damage.
 
Fatigue
 
Redness of irritation of the skin in the treatment area
 
Hair loss in the treatment area
 
Some soreness of the ribs with an increased risk of rib fracture.
 
	Less common (<10% of patients): 
 
Difficulty breathing, increased shortness of breath
 
Fever
 
Fracture or compression of the treated bones of the spine, which can result in pain and may need surgical treatment
 

Rare (<1% of patients)	

Some patients can have the following symptoms associated with lung scarring:
 
 
Shortness of breath, cough, fever, and/or pain in the chest wall.
 
These patients may require oxygen for a short time or permanently.
 
Lung damage can be life threatening.
 
Pericarditis
 
Damage to the heart muscle, which can cause heart attack, heart failure, or death
 
Damage to the spinal cord, which can cause numbness, weakness, tingling, and/or inability to use the arms and/or legs
 
Damage to the esophagus, which can cause problems with swallowing
 
Damage to the stomach or bowel which can lead to ulceration or perforation with a risk of infection and death.
 
Damage to the large blood vessels surrounding the heart, which could cause coughing up of blood and possibly death
 
Severe pain or skin damage leading to an open wound.
 
The following are likely with SBRT to the bones of the spine in the neck:
 
Inflammation of the lining of the mouth and esophagus
 
Inflammation of the vocal cords, leading to hoarseness or loss of voice
 
	
Risks and side effects related to non-SBRT or more "fractionated" radiation to the chest:	
More common (>10% of patients): 
 
Temporary, difficulty, pain, or a burning sensation when swallowing
 
Temporary fatigue
 
Tanning, redness of the skin, and hair loss within the treatment area, Skin in the treatment area may remain permanently dry
 
chest hair may not grow back
 
Decrease in blood counts while undergoing treatment causing bleeding, and bruising
 
Cough and some difficulty in breathing due to lung damage
 
	Less common (<10% of patients): 
 
Narrowing of the esophagus causing difficulty swallowing (rarely requiring internal dilation or a feeding tube)
 

Rare but serious (late) (<1% of patients)	

 
Pericarditis – irritation of the heart sac causing a rapid heart rate, or chest pain.
 
Myocarditis – irritation of the heart muscle causing shortness of breath, chest pain, or permanent heart muscle damage
 
Transverse myelitis – irritation of the spinal cord causing weakness or paralysis
 
Bleeding from the airway
 
Narrowing of the airway causing shortness of breath
 
	

**9.2 Adverse Event List for Pembrolizumab**

In general, immunotherapy has a risk (>10%) of developing autoimmune complication(s), such as inflammation of the thyroid (hypothyroidism or hyperthyroidism), colon (colitis), lungs (pneumonitis), liver (hepatitis), or pituitary gland (hypophysitis), which can lead to the symptoms noted below. Autoimmune complications can potentially be life-threatening or permanent. In some cases they may be reversible with urgent administration of steroids and/or other immunosuppressant(s).
	
More common (>10% of patients): 
 
constipation
 
depressed mood
 
diarrhea
 
dry skin and hair
 
feeling cold
 
flushing
 
hair loss
 
hoarseness or husky voice
 
	Less common (<10% of patients): 
 
general feeling of discomfort or illness
 
fever
 
nervousness
 
pain symptoms
 
sensitivity to heat or cold
 
slowed heartbeat
 
stomach cramps
 
sweating
 

A Randomized Trial of Consolidative Immunotherapy with vs without Thoracic Radiotherapy and / or Stereotactic Body Radiation Therapy (SBRT) after First-line Systemic Therapy for Metastatic NSCLC  
Wake Forest Baptist Comprehensive Cancer Center  
WFBCCC # 62718

• joint or muscle pain

• muscle cramps or stiffness

• skin rash or itching

• unusual tiredness or weakness

• stuffy or runny nose

	

• swelling of the face, feet, or lower legs

• tenderness

• cough or thickening of bronchial secretions

• trouble breathing, chest pain, or chest tightness

• trouble sleeping

• upper right abdominal or stomach pain

• watery or bloody diarrhea

• weight change

• yellow eyes and skin


Rare (<1% of patients)
 

• bloating

• dark, bloody, or cloudy urine

• blurred vision or other change in vision

• darkening of the skin

• dizziness

• drowsiness

• eye pain

• fainting

• fast heartbeat

• indigestion

• loss of appetite

• mental depression

• nausea or vomiting

• pains in the stomach, side, or abdomen, possibly radiating to the back

• redness or irritation of the eye

• sensitivity of the eye to light

• skin blistering, peeling, loosening, or tearing

	

### 9.3 Adverse Event Characteristics

**CTCAE term (AE description) and grade:** The descriptions and grading scales found in the revised NCI Common Terminology Criteria for Adverse Events (CTCAE) version 5.0 will be utilized for AE reporting. All appropriate treatment areas should have access to a copy of the CTCAE version 5.0. A copy of the CTCAE version 5.0 can be downloaded from the CTEP web site (<http://ctep.cancer.gov>).

**'Expectedness':** AEs can be 'Unexpected' or 'Expected' (see Appendix D) for expedited reporting purposes only.

**Attribution of the AE:**

Definite – The AE is **clearly related** to the study treatment.

Probable – The AE is **likely related** to the study treatment.

Possible – The AE **may be related** to the study treatment.

Unlikely – The AE is **doubtfully related** to the study treatment.

Unrelated – The AE is **clearly NOT related** to the study treatment.

### 9.4 DSMC SAE Reporting Requirements

The Data and Safety Monitoring Committee (DSMC) is responsible for reviewing SAEs for WFBCCC Institutional studies as outlined in [Appendix D](#). DSMC currently requires that all unexpected 4 and all grade 5 SAEs on these trials be reported to them for review. All WFBCCC Clinical Protocol and Data Management (CPDM) staff members assisting a Principal Investigator in investigating, documenting and reporting an SAE qualifying for DSMC reporting are responsible for informing a clinical member of the DSMC as well as the entire committee via the email notification procedure of the occurrence of an SAE.

### 9.5 WFUHS IRB AE Reporting Requirements

Any unanticipated problems involving risks to subjects or others and adverse events shall be promptly reported to the IRB, according to institutional policy. Reporting to the IRB is required regardless of the funding source, study sponsor, or whether the event involves an investigational or marketed drug, biologic or device. Reportable events are not limited to physical injury, but include psychological, economic and social harm. Reportable events may arise as a result of drugs, biological agents, devices, procedures or other

A Randomized Trial of Consolidative Immunotherapy with vs without Thoracic Radiotherapy and / or Stereotactic Body Radiation Therapy (SBRT) after First-line Systemic Therapy for Metastatic NSCLC  
Wake Forest Baptist Comprehensive Cancer Center  
WFBCCC # 62718

interventions, or as a result of questionnaires, surveys, observations or other interactions with research subjects.

All members of the research team are responsible for the appropriate reporting to the IRB and other applicable parties of unanticipated problems involving risk to subjects or others. The principal investigator, however, is ultimately responsible for ensuring the prompt reporting of unanticipated problems involving risk to subjects or others to the IRB. The principal investigator is also responsible for ensuring that all reported unanticipated risks to subjects and others which they receive are reviewed to determine whether the report represents a change in the risks and/or benefits to study participants, and whether any changes in the informed consent, protocol or other study-related documents are required.

Any unanticipated problems involving risks to subjects or others occurring at a site where the study has been approved by the WFUHS IRB (internal events) must be reported to the WFUHS IRB within 7 calendar days of the investigator or other members of the study team becoming aware of the event.

Any unanticipated problems involving risks to subjects or others occurring at another site conducting the same study that has been approved by the WFUHS IRB (external events) must be reported to the WFUHS IRB within 7 calendar days of the investigator or other members of the study team becoming aware of the event.

Any event, incident, experience, or outcome that alters the risk versus potential benefit of the research and as a result warrants a substantive change in the research protocol or informed consent process/document in order to insure the safety, rights or welfare of research subjects.

## **9.6 Study Management**

**9.6.1** Personnel from the Comprehensive Cancer Center at the Wake Forest University Health Sciences will monitor the trial. All case report forms and source documentation must be sent to Wake Forest University Health Sciences for review by the Clinical Research Associates to assure proper conduct of the trial and proper collection of the data. Queries will be issued to the site by WFUHS which should be addressed in a timely manner.

### **9.6.2 Required Documentation**

- 9.6.2.1 Before the study can be initiated at any site, the following documentation must be provided to the Clinical Research Management Office of Wake Forest University Health Sciences.
- 9.6.2.2 A copy of the official IRB approval letter for the protocol and informed consent
- 9.6.2.3 CVs and medical licensure for the principal investigator and any associate investigators who will be involved in the study
- 9.6.2.4 A copy of the IRB-approved consent form
- 9.6.2.5 CLIA Laboratory certification and institution lab normal values

### **9.6.3 Amendments to the Protocol**

- 9.6.3.1 Should amendments to the protocol be required, the amendments will be originated and documented by the principal investigator at WFUHS. It should also be noted that when an amendment to the protocol substantially alters the study design or the potential risk to the patient, a revised consent form might be required.

**9.6.4 Study Monitoring / Auditing Procedure**

9.6.4.1 Personnel from CCCWFU will monitor periodically to assure proper conduct of the trial and proper collection of the data. The investigator at the site will allow the monitor to review all source documents used in the preparation of the case reports. The Protocol office at CCCWFU can be reached at [name]. The Affiliate site will be audited via scanning all protocol related documents (charts, regulatory, drug logs etc.) and emailing them to the study team at the designated time which will be determined by the principal investigator and communicated to the site by letter. The study team will consist of the principal investigator, study staff and other designated individuals as needed. The site will be given at least 4 weeks' notice. The affiliate site must have persons(s) available via phone during the audit process if questions arise.

9.6.4.2 The overall study principal investigator will review with the affiliate principal investigator the scoring of patient response or progression on a periodic basis once accrual has commenced at that site either through site visit or electronic means.

**9.6.5 Record Retention**

9.6.5.1 Study documentation includes all case report forms, data correction forms or queries, source documents, correspondence, monitoring logs/letters, and regulatory documents (e.g., protocol and amendments, IRB correspondence and approval, signed patient consent forms).

9.6.5.2 Source documents include all recordings of observations or notations of clinical activities and all reports and records necessary for the evaluation and reconstruction of the clinic research study.

9.6.5.3 Regulations and directives require that all study documentation pertaining to the conduct of a clinical trial must be retained by the study investigator. Study documents should be kept on file until six years after the completion and final study report.

**9.6.6 Obligations**

9.6.6.1 The principal investigator is responsible for the conduct of the clinical trial at the site in accordance with title 21 of the Code of Federal Regulations and/or the Declaration of Helsinki. The principal investigator is responsible for personally overseeing the treatment of all study patients. The principal investigator must assure that all study site personnel, including sub-investigators and other study staff members, adhere to the study protocol all regulations and guideline regarding clinical trials both during and after study completion.

9.6.6.2 The principal investigator at each institution or site will be responsible for assuring that all the required data will be collected and entered onto the Case Report forms. Periodically, monitoring contacts will be made and the principal investigator will provide access to his/her records for verification of proper data entry. At the completion of

A Randomized Trial of Consolidative Immunotherapy with vs without Thoracic Radiotherapy and / or Stereotactic Body Radiation Therapy (SBRT) after First-line Systemic Therapy for Metastatic NSCLC  
Wake Forest Baptist Comprehensive Cancer Center  
WFCCC # 62718

the study, all case reports forms will be reviewed by the principal investigator.

## 10.0 Data Management

If technically feasible at the time that this study begins, we will allow outside institutions remote access to our Wake Forest OnCore program for direct data entry and randomization. Otherwise, all institutions will provide registration information to the Wake Forest protocol registrar and will be assigned randomization through the Wake Forest OnCore program. All other data collected as per the appendices below will be provided directly to [name] by fax or email: [REDACTED] [REDACTED]

Informed consent document	EPIC
Protocol registration form	WISER/OnCore
Adverse Events Log	WISER/OnCore
30-day Treatment Follow-up	WISER/OnCore
Off-Study Form	WISER/OnCore
Treatment Response Evaluation Form	WISER/OnCore
Evaluation of Best Overall Response	WISER/OnCore
NCI Comorbidity Index	WISER/OnCore
Radiotherapy Technical Parameters	WISER/OnCore
Patient Baseline Characteristics	WISER/OnCore
Pulmonary Function Testing	WISER/OnCore
Protocol Deviation Form	WISER/OnCore
Follow-up Collection Form	WISER/OnCore
Study Incomplete/Withdrawal Form	WISER/OnCore
Withdrawal of Consent	WISER/OnCore
Survival Form	WISER/OnCore
Off-Treatment Form	WISER/OnCore

## 11.0 Pharmaceutical Information

### 11.1 Pharmaceutical Accountability

Pembrolizumab is commercially available

### 11.2 Pembrolizumab FDA pharmaceutical information (Keytruda)

#### Product description:

Pembrolizumab is a humanized monoclonal antibody that blocks the interaction between PD-1 and its ligands, PD-L1 and PD-L2. Pembrolizumab is an IgG4 kappa immunoglobulin with an approximate molecular weight of 149 kDa.

KEYTRUDA for injection is a sterile, preservative-free, white to off-white lyophilized powder in single-use vials. Each vial is reconstituted and diluted for intravenous infusion. Each 2 mL of reconstituted solution contains 50 mg of pembrolizumab and is formulated in L-histidine (3.1 mg), polysorbate 80 (0.4 mg), and sucrose (140 mg). May contain hydrochloric acid/sodium hydroxide to adjust pH to 5.5.

KEYTRUDA injection is a sterile, preservative-free, clear to slightly opalescent, colorless to slightly yellow solution that requires dilution for intravenous infusion. Each vial contains 100 mg of pembrolizumab in 4 mL of solution. Each 1 mL of solution contains 25 mg of pembrolizumab and is formulated in: L-histidine

(1.55 mg), polysorbate 80 (0.2 mg), sucrose (70 mg), and Water for Injection, USP.

**Solution preparation:**

Reconstitution of KEYTRUDA for Injection (Lyophilized Powder) • Add 2.3 mL of Sterile Water for Injection, USP by injecting the water along the walls of the vial and not directly on the lyophilized powder (resulting concentration 25 mg/mL).

Slowly swirl the vial. Allow up to 5 minutes for the bubbles to clear. Do not shake the vial.

**Preparation for Intravenous Infusion**

Visually inspect the solution for particulate matter and discoloration prior to administration. The solution is clear to slightly opalescent, colorless to slightly yellow. Discard the vial if visible particles are observed.

Dilute KEYTRUDA injection (solution) or reconstituted lyophilized powder prior to intravenous administration.

Withdraw the required volume from the vial(s) of KEYTRUDA and transfer into an intravenous (IV) bag containing 0.9% Sodium Chloride Injection, USP or 5% Dextrose Injection, USP. Mix diluted solution by gentle inversion. The final concentration of the diluted solution should be between 1 mg/mL to 10 mg/mL.

Discard any unused portion left in the vial

**Storage requirements:**

Do not freeze. The product does not contain a preservative. Store the reconstituted and diluted solution from the KEYTRUDA 50 mg vial either:  
• At room temperature for no more than 6 hours from the time of reconstitution. This includes room temperature storage of reconstituted vials, storage of the infusion solution in the IV bag, and the duration of infusion.

• Under refrigeration at 2°C to 8°C (36°F to 46°F) for no more than 24 hours from the time of reconstitution. If refrigerated, allow the diluted solution to come to room temperature prior to administration.

Store the diluted solution from the KEYTRUDA 100 mg/4 mL vial either:  
• At room temperature for no more than 6 hours from the time of dilution. This includes room temperature storage of the infusion solution in the IV bag, and the duration of infusion.  
• Under refrigeration at 2°C to 8°C (36°F to 46°F) for no more than 24 hours from the time of dilution. If refrigerated, allow the diluted solution to come to room temperature prior to administration.

**Stability:**

Include the stability of the original dosage form, reconstituted solution, and final diluted product, as applicable

**Route of administration:**

Administer infusion solution intravenously over 30 minutes through an intravenous line containing a sterile, non-pyrogenic, low-protein binding 0.2 micron to 5 micron in-line or add-on filter. Do not co-administer other drugs through the same infusion line.

**Disposal:**

Dispose of per the Wake Forest waste stream

## 12.0 Laboratory Correlative Studies

### 12.1 Future exploratory blood biomarker studies

Wake Forest (the sponsor) will conduct future biomedical research on blood and tumor tissue samples collected during this clinical trial. This research may include genetic analysis to be used for exploratory biomarker testing or analysis of circulating tumor cell DNA.

Samples will be stored in the Wake Forest biorepository

Common side effects of a biopsy or blood draw are a small amount of bleeding at the time of the procedure, pain at the biopsy site, which can be treated with regular pain medications, and bruising. Rarely, an infection can occur. In the event of recurrence, an additional biopsy to confirm the pathology of disease is strongly recommended. In the event that a biopsy is performed, as part of standard of care, a portion of the tumor sample will be sent to the Wake Forest Tumor Bank.

Submission of blood and tissue samples for future biomedical research is a required component of this protocol.

Two tubes of whole blood will be collected via routine blood draw and saved for future exploratory biomarker studies. These may be collected at time of registration or any time prior to initiating any protocol directed therapy and at the 1 month follow up +/- 2 weeks. Patients would routinely have standard bloodwork performed at these time points off protocol and this will not require extra visits.

## 13.0 Statistical Considerations

### 13.1 Power and Sample size

Based on previously published research and clinical experience, the predicted median progression-free survival (PFS) of patients treated with consolidation immunotherapy without SBRT is roughly 8 months measured from date of first chemo-immunotherapy treatment. We estimate that, considering this 8 month median survival in the “control” arm, with our projected sample size of 112 patients (randomized 2:1 to SBRT + immunotherapy vs immunotherapy alone), and considering a two-sided alpha of 0.05 and power of 0.80, that we will be able to detect a median survival of approximately 15 months from start of chemo-immunotherapy in the SBRT + immunotherapy arm. This calculation assumes a 54 month accrual period and a 5 year total follow-up period. This difference in median survivals (8 months vs 15 months) corresponds to a hazard ratio of 0.53. Randomization will be stratified by number of metastatic sites (1-3, 4-6, or 7-8.)

Given the design of this trial, not all enrolled patients will be eligible for subsequent randomization. We estimate that ~10% may have evidence of progression of disease on restaging with PET/MRI. Such patients would remain on study, but will only be followed for survival. Given this potential for a 10% decrease in randomizable patients, the final number needed to enroll is 125, in order to randomize 112.

### 13.2 Estimated Accrual Rate

We estimate that we will accrue roughly 1 - 4 patients per month.

**13.3 Estimated Study Length**

We estimate approximately 4- 5 years for total enrollment. Data will be collected until patient death or for a period of 5 years whichever occurs first.

**13.4 Interim Analysis Plan**

We have no planned formal interim analyses; however when we reach 50% of our planned accrual if 25% or greater have reached G3 or higher pneumonitis we will halt the study.

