**What is considered as an Unexpected Grade 4 event?**

Any grade 4 event that was not specifically listed as an expected adverse event in the protocol should be considered as unexpected. A grade 4 adverse event can be considered to be unexpected if it is an event that would not be expected based on the treatment being received or if it is unexpected based on the health of the patient. In either case, if there is any uncertainty about whether a grade 4 adverse event is expected or unexpected it should be reported to DSMC.

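### The only rate-based pneumonitis rule is applied once, at half accrual: about 37 patients are assigned radiation before it can act, and no rate boundary covers the roughly 38 who follow.

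*Combined protocol and SAP*

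**What the plan says.** Section 13.4 opens with "We have no planned formal interim analyses" and then gives one safety condition: "however when we reach 50% of our planned accrual if 25% or greater have reached G3 or higher pneumonitis we will halt the study". It does not say who forms the denominator, how much follow-up a counted patient must have, or whether accrual pauses for the check.

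Section 13.1 sets 112 randomized patients, allocated 2:1 in favour of radiation, and adds: "This calculation assumes a 54 month accrual period". For the loss between enrollment and randomization it states that "the final number needed to enroll is 125, in order to randomize 112".

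A second safety route runs through the DSMC. Appendix R requires three kinds of event to be reported during treatment or within 30 days of the last study treatment: unexpected grade 4 events, deaths, and unplanned admissions longer than 24 hours whatever the grade. On expectedness it says: "Any grade 4 event that was not specifically listed as an expected adverse event in the protocol should be considered as unexpected". The same paragraph allows a grade 4 event to be unexpected because of the patient's health, and sends doubtful cases to the DSMC. Each report must record whether the protocol should be suspended, and the DSMC may suspend the trial. Section 9.4 describes the same duty but lists only unexpected grade 4 and grade 5 events.

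**The concern.** Grade 3 or higher pneumonitis is the one toxicity for which the sponsor set a numerical limit. Section 1.7 records the worry that radiation plus immunotherapy could over-stimulate the immune response. It supports safety with a study that treated 1-3 sites, whereas this trial allows up to eight.

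A rule with one look cannot act during the first half, when acting would spare the most patients. If the count falls just short, it is never tested again. Pneumonitis in patients irradiated shortly before the check, or at any time after it, never enters the rule. The DSMC route has no rate to compare with, and nobody is assigned to keep the running count.

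**Working it through.** **Inputs.** From Section 13.1: 112 randomized, 2:1, 54 months of accrual, 125 enrolled with 10% lost before randomization. From Section 13.4: one look at 50% accrual, threshold 25%. From Section 1.7: 3 grade 3 pneumonitis cases in 73 patients given SBRT and pembrolizumab (4.1%). Assumed: 75 irradiated patients in total, and only irradiated patients counted.

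**The plan's own figures.** The hazard ratio is 8/15 = 0.533. Events needed (Schoenfeld, 2:1): (1.96 + 0.842)² / [(2/9) × ln(0.533)²] = 89.4, so 90. Exponential survival with uniform accrual over 54 months and analysis at month 60 gives 86.5 expected events and power 0.787 (0.809 with the 1/d1 + 1/d2 variance). The stated 0.80 is reproduced closely. 112/0.90 = 124.4, so 125 enrolled.

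**Timing and counts.** Half accrual is 56 randomized, of whom 56 × 2/3 = 37.3 are in the radiation arm. The radiation arm totals 112 × 2/3 = 74.7, so about 37-38 follow the check. Counting enrolled patients instead gives 62.5 × 0.9 × 2/3 = 37.5. The check falls at 54/2 = month 27; the 4-5 years of enrollment in Section 13.3 give months 24-30.

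**Single look.** 25% of 37 is 9.25, so the trigger is 10. The chance of halting is P(X ≥ 10 | 37, p).

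**Four looks.** Looks at 12, 24, 37 and 56 irradiated patients, with a halt if cumulative events reach the limit. Exact binomial recursion, each event visible when the patient is counted:

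| True rate | Single look, 10/37 | Limits 6, 9, 11, 15 | Limits 5, 8, 10, 14 |
|---|---|---|---|
| 10% | 0.27% | 0.15% | 0.8% |
| 15% | 4.2% | 3.0% | 7.5% |
| 20% | 19.1% | 17.7% | 30% |
| 25% | 45% | 48% | 62% |
| 30% | 71% | 78% | 87% |

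**Patients treated at a true 40%.**
- Single look: 37 × 0.965 + 75 × 0.035 = 38.3 patients, and × 0.4 = 15.3 events.
- Limits 6, 9, 11, 15 (chance of stopping at each look 0.335, 0.354, 0.243, 0.057; never 0.011): 12 × 0.335 + 24 × 0.354 + 37 × 0.243 + 56 × 0.057 + 75 × 0.011 = 25.5 patients, 10.2 events, a saving of one third.
- Limits 5, 8, 10, 14: 20.1 patients, 8.1 events.

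**Delayed onset, true 40%.** Irradiated patients accrue at 75/54 = 1.39 per month, so a lag of 3 or 6 months (assumed) hides the last 4.2 or 8.3 of them.

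*Looks triggered by headcount.* The single look then sees 32 or 28 patients, and the four looks see 7, 19, 32, 51 or 3, 15, 28, 47. The same recursion gives:

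| Expected events | Single | 6, 9, 11, 15 | 5, 8, 10, 14 |
|---|---|---|---|
| No lag | 15.3 | 10.2 | 8.1 |
| 3 months | 16.6 | 14.8 | 12.6 |
| 6 months | 18.7 | 18.0 | 16.0 |

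*Looks triggered when the nth patient has completed the lag.* Each stop adds 4.2 or 8.3 patients, in either design. At 3 months: single 38.3 + 0.965 × 4.2 = 42.3 patients (16.9 events); limits 6, 9, 11, 15, 25.5 + 0.989 × 4.2 = 29.7 (11.9 events), a saving of 30%. At 6 months: 46.3 against 33.8 patients, 18.5 against 13.5 events, a saving of 27%.

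**If all 56 randomized patients are counted,** the trigger becomes 14. With an assumed 3% rate in the control arm, the single look halts with probability 0.09, 0.26 and 0.73 at true radiation-arm rates of 25%, 30% and 40%.

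**The case against.** The strongest reply is that the DSMC already watches this toxicity throughout, and much of that stands. A reader might infer from Section 13.4 that nothing can stop the trial before or after the half-way check. The documents do not support this: Appendix R requires a suspension judgement with every reported event and lets the DSMC suspend at any time.

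A reader might also infer that, because Section 9.2 lists pneumonitis, grade 4 cases count as expected and stay out of the DSMC's sight unless the patient is admitted or dies. That is too strong as well. Section 9.2 gives no grade, and Appendix R sends doubtful grade 4 cases for review. The table in Section 6.2 advises admission for grade 3-4 pneumonitis, and an unplanned admission over 24 hours is reportable. The reporting window covers all study treatment, and Section 8.5 refers to a total of 2 years of maintenance.

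Some gaps remain. The Section 6.2 guidance is not mandatory, so a grade 3 case without such an admission need not be reported. Nor need a case arising more than 30 days after the last treatment. Section 9.4 omits the admission criterion that Appendix R contains. None of this review compares a running rate with a limit.

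Two further objections are fair. Rates of 30-40% are far above the 4.1% in Section 1.7, so they are stress scenarios; at a true 5% neither kind of rule would practically ever fire. And it would be wrong to say that repeated looks simply halve the toxicity. The 15.3 to 8.1 reduction needs the loose limits and instantly visible events. With headcount looks and those limits the saving falls to about 24% (3-month lag) or 14% (6-month lag), and the same limits raise the chance of halting at a true 20%, still below the sponsor's threshold, from 19% to 30%.

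**Conclusion.** The point holds as a limitation of the rule in Section 13.4. It has one look, about 37 patients are assigned radiation before it, and no rate boundary applies to the roughly 38 after it. DSMC review softens this but does not replace a rate boundary.

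The improvement need not be paid for in false halts. With limits 6, 9, 11 and 15 the chance of halting is slightly lower than now at true rates of 10%, 15% and 20%, and higher at 25% and above. The gain is modest at 30% (71% to 78%) and larger at 40% (about 13 fewer patients treated and 5 fewer events). Under delayed onset most of it survives only if the looks are timed on patients with adequate follow-up; with headcount looks and a 6-month lag it nearly disappears.

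These sizes rest on irradiated-only counting with a trigger of 10/37, 75 irradiated patients and assumed lags. Month 27 also assumes uniform accrual. The sponsor should make the change, but the trial is not without protection in its absence.

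**What to change.** Rewrite Section 13.4 so that the rule:
- names its denominator (irradiated patients are assumed here) and the follow-up a patient needs before being counted;
- is applied at several pre-specified counts, for example 12, 24, 37 and 56, with at least one look in the second half;
- states the pneumonitis rate regarded as acceptable, and sets limits so that the false-halt chance is no higher than under the present single look. Limits of 6, 9, 11 and 15 illustrate this; as proportions they are 50%, 38%, 30% and 27%, stricter evidence early and close to the sponsor's 25% later;
- sends the running count of all grade 3 or higher pneumonitis, admitted or not, to the DSMC at each look.

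Section 9.4 and Appendix R should be reconciled on whether unplanned admissions are reportable.

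The cost is wording and several tallies instead of one; the calendar in Section 8.1 already grades toxicity at each follow-up visit. Looser limits such as 5, 8, 10 and 14 protect more, but raise the chance of halting to 7.5% at a true 15% and 30% at a true 20%, a trade the sponsor would have to choose openly.
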